## 1.0 CHAPTER ONE: Introduction and Background

Preterm birth is responsible for 1/3 of paediatric deaths under age five.[2] Infants born very early suffer from respiratory distress syndrome due to under developed lungs and this is a leading cause of their deaths.[3] An additional 15% of children under age five die from trouble breathing due to respiratory tract infections such as pneumonia.[2] Continuous positive airway pressure (CPAP) provides constant distending pressure to the lungs and decreases the work of breathing for an infant. It is the recommended standard of care for respiratory failure caused by respiratory distress syndrome or pneumonia, and should be started as soon as the diagnosis is made.[4,5] The pressure provided by bubble CPAP (bCPAP) is regulated by the depth of the tube in the water bottle. The gas flow through the tube creates bubbling, and the resulting oscillations are helpful to a patient's lungs. Because of this, bCPAP is considered superior to standard CPAP in treating neonatal respiratory failure. Commercialized devices are available (Figure 1)[6], but are rarely found in resource constrained settings due to the prohibitive cost.

[figure not shown]

Figure 1. Commercialized bubble CPAP (bCPAP) circuit. These systems can cost up to 10,000USD. Figure from: [7]

Commercialized devices considered to be “low cost” do exist, however, at a price of US\$900, resource-constrained sites still cannot afford them or cannot afford enough devices for the number of patients requiring treatment.[8] To address this care gap, the World Health Organization (WHO) recommends creating improvised bubble CPAP (bCPAP) devices using components available in the hospital, specifically tubing connected to bottles, with water to generate the necessary pressure.[7] (Figure 2). These improvised kits, however, have variable performance in terms of pressure delivered due to the variation in the diameter and length of available tubing, lack of appropriate cannulae sizes, and incorrect assembly of parts.

[figure not shown]

Figure 2. Improved bCPAP created from a simple nasal cannula, as advised by the WHO. Although lifesaving, this system runs on 100% oxygen which can be toxic to patients. Figure from [7].

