### 3.3 Study Product

#### Overview

The PATH bCPAP kit with oxygen blenders is intended to provide respiratory support to a neonate in respiratory distress where higher level means of respiratory support are not available. (See Appendix A for product label and instructions for use). This product is a single-use device for the purposes of this study. No changes to device design will be made during the study.

PATH's fixed-ratio, in-line oxygen blenders are small, single-use, injection moulded devices intended to provide a stable blend of air and oxygen to a neonate on bCPAP therapy. (Instructions for use in Appendix A). A blender is inserted (in-line) into the inspiratory limb of a bCPAP respiratory circuit and works by entraining room air into a stream of pressurized oxygen (based on the Bernoulli principle), producing a gently pressurized and blended gas that is delivered to the neonate (see Figures 4 and 5). The device provides a fixed ratio of air and oxygen that is consistent over the entire range of clinically relevant pressures (3 to 10 cmH2O) and remains consistent despite changes in flow (1 to 10 LPM). The blend is stable within  $\pm 5\%$  of the blender's nominal blend-ratio when used with 100% oxygen source, irrespective of the flow and pressure from the oxygen source, or the flow and pressure of the blended gas delivered to the neonate.

**Figure 5. Diagram showing the components of the PATH bCPAP circuit (tubing, cannula and bubbler) as well as placement of PATH oxygen blenders**

Flow and pressure of the blended gas are adjusted in the same manner as respiratory circuits containing no blender (i.e., by adjustment of the flow of gas entering the system and depth of the bubbler straw within the bCPAP bottle, respectively). To change the blend ratio, the blender is simply replaced with another to achieve a higher or lower percentage of oxygen delivered. Currently two fixed-ratio blenders have been developed; a “low blender” with a blend-ratio of 37% and a “high” blender with a blend-ratio of 60% (see Figure 6). The rationale for having two blends for this study is two-fold: (1) more blend ratios would complicate the decision-making process by the healthcare worker and (2) more blend ratios could increase the amount of time spent swapping out blenders. However, additional blend ratios between 37% and 60% can be produced if this study suggests that more blending options would be of benefit.

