### 5.7.2 Tools

See “Data Collection Forms” in Appendix D, these include:

- Patient Data Form 1 (Demographics and Admission Clinical Data)
- Patient Data Form 2 (Clinical Course and bCPAP Settings)
- Concentrator FIO2 Output Form
- Newborn Unit Shift Form
- Adverse Event Record
- Unanticipated Adverse Device Effects (UADE) Event Record
- Healthcare Worker (HCW) Usability Form
- Healthcare Worker (HCW) Observation of bCPAP With or Without Blenders Set-up Form
- Healthcare Worker (HCW) Initial Interview Guide
- Healthcare Worker (HCW) Follow-Up Interview Guide

Data will be collected on the forms at the following timepoints:

Table 10. Patient Specific Data Collection Timing:

Form	Event					
	bCPAP initiation	Blender start or change	bCPAP pressure change	bCPAP stopped	Patient discharged/ deceased	Unanticipated Adverse Device Effect or Adverse Event
Healthcare Worker (HCW) Observation of bCPAP With or Without Blender Set-Up	X					
Patient Data Form 1 (Demographics)	X			X	X	

and Admission Clinical Data)						
Patient Data Form 2 (Clinical course and bCPAP settings)	X	X	X	X		
Adverse Event Record						X
Unanticipated Adverse Device Effects (UADE) Event Record						X

Table 11. Unit/Equipment Specific Data Collection Timing:

	Each Shift	Each Week
Newborn Unit Shift Form	X	
Concentrator FIO 2 Output Form		X

Table 12. Nursing Specific Data Collection Timing:

	With Each PATH bCPAP initiation	Initial Interview	Final Interview
HCW Initial Interview Guide		X	
HCW Follow-up Interview Guide			X
HCW Usability Form	X		

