### 5.8.2 Data analysis

Table 13 presents a summary of variables, data sources and analysis plan. We will evaluate operational feasibility by analysing the domains below; each domain uses information from mixed data sources. We will create an index measure for each domain, all of which will be weighted equally. We will sum these index measures to determine overall operational feasibility.

- Ease of correct use: Median set-up time, frequency of correct set up, time to change blender, types and frequencies of user errors, frequency of changes to blend provided per day, frequency of bCPAP level adjustment per day
- Integration into service delivery: Count of patients treated with PATH bCPAP, Frequency of blending via air compressor and PATH blenders, Frequency of known bCPAP complications
- Confirmation of device functionality: Median and IQR of: FIO2 administered by PATH blenders (determined by blender used and FIO2 provided by concentrator), level of bCPAP (and min/max), total air/oxygen flow to bCPAP device (subset)
- Concentrator output: Ability to determine FIO2 delivered to patient
- Device malfunction: Frequency of device malfunctions with and without adverse events

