#### **Mild Physical Risks:**

- Nasal irritation: A bCPAP system uses a nasal cannula as the patient interface. It is important that the cannula have a close fit in the nasal openings to prevent any loss of pressure. Multiple sizes of cannula are provided in the PATH kit to allow proper sizing for each patient. There is a risk of skin irritation from the nasal cannula due to rubbing or pressure from the cannula on surrounding areas. Standard of care for a patient on bCPAP therapy includes skin assessments every 3 hours. Proper sizing and positioning of the cannula, along with diligent skin care can prevent this complication.
- Abdominal distention: The bCPAP system works by administering a gentle flow of pressure into the infant's lungs to help them breath. An unavoidable but mild complication results from the flow of pressure that also enters the oesophagus and into the stomach. Accumulation of air in the stomach can lead to mild distention of the abdomen. An orogastric tube inserted into the patient's stomach and attached to an empty syringe (no plunger) will help eliminate any accumulated air. Positioning the patient to rest in a prone position can also help with abdominal distention.

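### The bCPAP level listed under device functionality appears to be the level staff set, so its summary does not directly show whether the circuit delivers pressure

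*Combined protocol and SAP*

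**What the plan says.** Section 5.8.2 builds operational feasibility, the first primary objective, from five equally weighted domain indices that are summed. The third domain opens "Confirmation of device functionality: Median and IQR of: FIO2 administered by PATH blenders" and continues with "level of bCPAP (and min/max" and total gas flow into the device in a subset. The section does not define the level of bCPAP. It gives no target, tolerance or scoring rule for it.

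Other parts of the protocol say where the level comes from:

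- Chapter One: "The pressure provided by bubble CPAP (bCPAP) is regulated by the depth of the tube in the water bottle".
- Section 3.3, Overview: flow and pressure are changed "by adjustment of the flow of gas entering the system and depth of the bubbler straw within the bCPAP bottle, respectively".
- Section 5.8.2, ease-of-use domain: "frequency of bCPAP level adjustment per day" is counted among the things users do.
- Section 5.7.2: the form that would hold the level is "Patient Data Form 2 (Clinical Course and bCPAP Settings"). Table 13 names the same form as a source for Objective 1.

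**The concern.** A domain that claims to confirm function should contain measurements that come out differently when the function fails. A set depth is an input chosen by the nurse. Its median, IQR and range describe practice on the unit. They do not depend directly on whether gas leaks at the nose, an adapter is loose or the circuit is under-driven.

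The protocol recognises that set and delivered pressure can part company. In section 5.9.3 it notes: "It is important that the cannula have a close fit in the nasal openings to prevent any loss of pressure". Table 6 tells staff to check connections and the nasal interface when saturation falls. Chapter Two gives accurate pressure delivery as a reason for needing a tested low-cost design. A reader of the final report could therefore take a plausible median level under this domain as evidence that pressure was delivered to infants, which the item cannot supply.

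**Working it through.** The plan states no figure to reproduce, and section 5.3 says that the sample size is not hypothesis driven. The check is therefore a trace of the variable, followed by a small illustration.

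**Trace**

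1. *What is analysed:* level of bCPAP, by median, IQR and min/max (section 5.8.2).
2. *Where it is recorded:* of the three sources that Table 13 lists for Objective 1, the matching one is Form 2, whose title refers to settings. The others are the set-up observation form and the concentrator output form.
3. *When it is recorded:* Table 10 calls for Form 2 at initiation, blender start or change, pressure change, and stopping. A pressure change is treated as an event that triggers an entry. No scheduled reading is shown, so pressure lost without a staff adjustment triggers no entry.
4. *What fixes the value:* straw depth, chosen by staff (Chapter One; section 3.3).
5. *Any measurement of delivered pressure:* the visible text describes no manometer, no reading in the circuit or at the nose, no recorded bubbling check, and no comparison of set with delivered pressure. Table 2 lists no gauge, but it covers kit components and not study instruments, so this adds little.
6. *The companion items:* FIO2 is derived from the blender used and the concentrator output. Total flow is taken in a subset of unstated size. Neither is a pressure.

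**Illustration.** All values are assumed: 40 infants, set levels drawn from 5, 6, 7 and 8 cmH2O, recorded level = set level, and delivered level = set level × (1 − loss). At the median, for example, 6 × (1 − 0.25) = 4.5.

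| Loss | Recorded median (IQR; min–max) | Delivered median (IQR; min–max) |
|---|---|---|
| 0% | 6 (6–8; 5–8) | 6 (6–8; 5–8) |
| 25% | 6 (6–8; 5–8) | 4.5 (4.5–6; 3.75–6) |
| 50% | 6 (6–8; 5–8) | 3 (3–4; 2.5–4) |
| 100% | 6 (6–8; 5–8) | 0 (0–0; 0–0) |

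The recorded column is constant by definition once the recorded value is the set value and staff do not react. If staff react to a leak by raising the setting, the recorded level would rise while delivery fell, so it would still not track delivery.

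**Share of the index.** The item is one of three in one of five equally weighted domains. If the three shared their domain equally, which the plan does not say, the item would carry 1/3 × 1/5 = 1/15, about 7%, of the total.

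**The case against.** Four arguments on the other side have weight.

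- *The level might be measured.* Section 5.8.2 does not define it, says that domains draw on mixed sources, and relies on forms in Appendix D that are not available. This stands, and it makes the conclusion conditional.
- *Failure is not invisible to the plan.* Low flow could show in the flow subset, and a loose adapter or leak could be counted in the separate malfunction domain. Incorrect set-up and user errors are recorded under ease of use, and research assistants alert staff to incorrect set-up. This also stands. However, none of these measures pressure, the set-up form is scheduled only at initiation, and malfunction has no pressure-based definition.
- *Pressure performance belongs to the bench.* Section 3.3 says that the study is not meant to confirm safety or efficacy. That supports describing the levels used, but it argues against placing them under a heading of confirmation. The visible Table 1 concerns the blenders. The verification report for the kit (Appendix B) is not available and may cover pressure. Bench work also cannot show cannula fit on an infant, while section 5.1 lists anatomical limitations among the things to be learned.
- *Cannula leak is not specific to the PATH kit.* Section 5.5 says that both kits use the same cannula, and section 5.9.3 mentions loss of pressure as something that close fit prevents. A reader might infer that the protocol reports leak as an established problem with this device. It does not.

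**Conclusion.** The point holds in conditional form. If Form 2 records the set depth and neither a measured pressure nor a bubbling check, this item describes settings used and carries no direct information on whether the circuit delivers pressure. Severity is minor to moderate: one item of three in one domain of five, in a primary objective, with no hypothesis test affected.

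Two stronger readings are tempting, and the documents do not support them. One is that the functionality domain counts pressure delivery as confirmed whatever happens. The plan gives no pass rule for the item, and the domain has two other items. The other is that the study would miss a pressure failure in every one of its up to 40 infants. The flow subset, malfunction counts, set-up observations and staff response could all reveal a gross failure.

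**What to change.** 1. In section 5.8.2, name the item set bCPAP level and report it as a description of use, outside the functionality index.
2. Under functionality, add a yes/no item for continuous bubbling to each existing Form 2 entry: initiation, blender start or change, pressure change, and just before stopping.
3. Report the share of entries with bubbling and the number of infants with at least one entry without it, split by whether a PATH blender was in line.
4. State that delivered pressure was not measured, that bubbling is only an indirect sign, and that losses between Form 2 entries are not captured. Because the form is event-driven, the count in item 3 is not a count of all infants who ever lost bubbling.
5. If Form 2 already records a measured pressure, say so in section 5.8.2 and report measured against set level instead.

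The cost is one tick box, filled in by research assistants who are already at the bedside around the clock in an observational role, plus a few sentences of text. Patient care is unchanged. Items 1 and 4 need only a text edit, and the relabelling and the statement on delivered pressure are worth making even if bubbling is not recorded.

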**Table 13. Summary of Relevant Data Analysis for Study Objectives**

Objective	Variables	Source of Data	Statistical analysis
Objective 1: To assess the operational feasibility of using the PATH bCPAP kit including, when appropriate, in-line oxygen	Observed use of kit by HCWs including completion of set-up steps, time to set-up, description of difficulties	
 
• Healthcare Worker (HCW) Observation of bCPAP With or Without Blender Set-Up
 
	
We will determine frequency of various parameters/variables collected on the use and set-up of the kit
 
Mean, standard deviations, medians and interquartile ranges will be used for

blending on neonatal patients		
 
• Patient data form 2 (clinical course and bCPAP settings)
 
• Concentrator FIO2 output form
 
	continuous variables based on their distribution
Objective 2: To assess the usability of the PATH bCPAP kit with oxygen blenders by healthcare workers.	Scores of usability by healthcare workers about ease of device set-up, learning the device, difficulty of use satisfaction with device and desire for continued use.	
 
• HCW usability form
 
	
We will use frequency table to summarize the responses on the Likert scale.
 
A total score generated by summing 10 items. Means, standard deviations and ranges will be reported.

Objective 2: To assess acceptability of the PATH bCPAP kit with oxygen blenders by healthcare worker.	Themes from HCW interview questions about what is liked best, least about the PATH bCPAP and blenders, ease-of-use initially and over time, difficulty of use, adequacy of blends available, adequacy of training, what could be changed, would HCW continue to use the PATH kit with or without blenders if they were available after the study end?	
 
• HCW Initial Interview Guide
 
• HCW Follow-up Interview Guide
 
	Notes from in-depth interviews will transcribed and imported in NVivo software, analysed using content and thematic techniques (mainly inductive approach)
Secondary objective: To report clinical characteristics, demographics and outcomes of patients treated with the PATH bCPAP kit and blenders in a newborn care unit in rural Uganda	Demographics and clinical characteristics	
 
• Patient Data Form 1 (Demographics and Admission Clinical Data)
 
	Frequencies, proportions and totals will be used to summarize categorical data with median and interquartile ranges for continuous variables.

## 5.9 Ethical considerations

### 5.9.1 Informed consent

Written, informed consent will be sought from the parents or legal guardian of every newborn started on bCPAP therapy, and who are available within 24 hours of initiation. When the legal guardians are available within 24 hours of bCPAP initiation, study personnel (nurses with experience in bCPAP therapy and blending, and fluent in Luganda) not caring for the infant will approach the legal guardians of eligible patients and inform them of the objectives of the research. Informed consent forms will be available in both English and Luganda and only IRB approved versions will be used. Study personnel obtaining consent will be fully trained on the recruitment and informed consent process and have human subjects research certification. The consent process is detailed in the Standard Operating Procedure for Obtaining Consent (Appendix E).

#### Patients:

Any patient who may benefit from care beyond that available at Kiwoko hospital are offered transfer (at their expense) to another facility. Meanwhile care for a newborn begins as soon as the patient is admitted. Using parental assent for admission and treatment is standard of care in the unit. Patients may require emergent initiation of bCPAP therapy due to respiratory failure. Patients often do not have a parent or legal guardian present at the time of bCPAP initiation, as the mother may still be in the operation theatre after a caesarean section, recovering from delivery, or away from the unit and unreachable by phone. In such instances, it is not appropriate to wait to obtain consent before the initiation of bCPAP therapy, as delaying the initiation of therapy could be life-threatening and would be contrary to WHO guidelines. (4)

**If the patient does not have a parent of legal guardian available at the time of admission,** standard of care will remain the same, and the patient will have bCPAP therapy initiated using the Kiwoko device as soon as it is clinically indicated. As soon as they are available to meet with study personnel, the parent or legal guardian will be approached for consent to the study and to the use of the PATH bCPAP kit and blender. Consent must be gained within 24 hours of bCPAP initiation to be eligible to participate in the study. If parents choose to consent, the Kiwoko bCPAP kit will be replaced with the PATH bCPAP kit and blender and the baby will be enrolled in the study. (Process described in section 5, study procedures).

**If a parent or legal guardian is available at the time of admission,** admitting staff will obtain an initial verbal consent from the parent to initiate them on the PATH bCPAP kit and blender. It may be inappropriate to pull the parents away for full consent at the time of admission due to: the time involved with obtaining the full consent process, the emergent nature of bCPAP therapy and the stress and pressure of having a sick newborn. In this instance, verbal consent will be gained. We will seek to obtain full written consent within 12 hours of receiving verbal permission. Please see the stand-alone verbal consent script, which is also included in the Consent Standard Operating Procedure (Appendix E). If after the full consent process, the parents no longer want to be a part of the study, the patient will be changed back to standard of care for the unit. The parents will receive a clear explanation of the alternative, including whether an air compressor is available for blending. If an air

compressor is not available at that time, we will state clearly that their baby may receive 100% oxygen and the potential consequences of such. Study information that has been gathered up to this point will not be retained by study personnel.

### **Formal consent process**

Study personnel (nurses with experience in bCPAP therapy and blending, and fluent in Luganda) not caring for the infant will inform parent or legal guardian of the objectives of the research and obtain consent. This consent will be obtained in a private location within the newborn unit as available. If the parent or legal guardian is unable to read, an impartial witness will be present to ensure they understand the study and their rights. Risks as well as benefits and alternatives to study participation will be discussed. The parent or legal guardian will be informed that if they decline study participation, the patient will be treated with Kiwoko bCPAP kit, and oxygen will be blended if an air compressor is available. Study personnel will ask for parents to explain back to them the study intervention. Consent forms will include a contact of the Makerere IRB chairperson. Consent will be documented with parental signature or thumbprint.

Parents will have access to in-unit study personnel 24x7 to ask further questions (in Luganda or English). The parent or legal guardian can withdraw from the study at any time during the study.

Determination of continued device use will be at the discretion of the attending medical provider.

